The intervention is a Hybrid Type 2 design, which means that we will compare the standard practice intervention (the state Quitline; Arm 1) with the expanded service alternative (the Quitline in addition to Smoke-Free Homes; Arm 2) among 1,980 low-income smokers across nine states. Participants will be randomly assigned to each Study Arm. The study outcomes are 7-day and 30-day point prevalence of smoking abstinence, number of cigarettes per day, number of 24-hour quit attempts, and acceptance of the interventions. Participants will be recruited from nine state United Way 2-1-1 agencies. The Quitline (standard service) will be delivered by our study partner Optum, a health-care services company that runs the state Quitlines. 2-1-1 callers who are daily smokers and interested in participating will be contacted by our study team who will conduct surveys by telephone with participants at Baseline, 3-month follow-up, and 6-month followup.

**1.4** Specify your research question(s), study aims or hypotheses:
 

**Aim 1:** Compare quit rates in Quitline only vs. Quitline + Smoke-Free Homes groups

- A. What proportion report 7-day and 30-day point prevalence abstinence at 3- and 6-month follow-up?
- B. What proportion report making a quit attempt (of at least 24 hours) at 3- and 6-month follow-up?
- C. What is the average change in cigarettes smoked per day at 3- and 6-month follow-up?
- D. Among those who decline Quitline services at baseline, what proportion report abstinence, quit attempts, and decrease in cigarettes smoked per day at 3- and 6-month follow-up?

**Aim 2:** Compare acceptance and use of Quitline services, and pro-cessation beliefs cumulatively over the study period in Quitline only vs. Quitline + Smoke-Free Homes groups.

- A. What proportion accept Quitline services?
- B. Among those who accept Quitline services, what proportion use 0, 1, or 2+ sessions of counseling?
- C. Among those still smoking at 6-month follow-up, how does readiness to quit, pessimism about quitting, and ambivalence about smoking differ by group?

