Participants in Arm 1 of the study will be offered standard service: their state's tobacco quitline. Participants in Arm 2 will be offered the quitline first and if they decline, they will be offered Smoke-Free Homes.

**1.8** Check all materials that will be used in recruiting participants:

- Telephone script

Attachment Name	Category	Version	Date Attached
2-1-1 screening for SFH UpdateTRACKCHANGES 5.14.21.rtf	Recruitment Script: Phone	7	05/14/21

**1.9** Describe where the consent discussion will occur (check all that apply):

- By phone

**1.10** Participants and/or their legally authorized representative will have (check all that apply to the consent process):

- As much time as they desire to consider enrolling in the study, including:

- An opportunity to thoroughly review the consent materials with knowledgeable members of the research team, and with family and/or friends as appropriate
- Sufficient time to have all of their questions answered

**1.11** Provide a detailed description in sequential order of the study procedures following the consent process - DO NOT cut and paste from the Consent Document.

Describe study populations separately if they will be participating in different procedures

DESCRIBE:

- Control populations, if applicable
- Any randomization, if applicable
- What participants will be asked to do/what happens in the study (in sequential order)
- The time period over which procedures will occur
- Long-term follow-up and how it occurs

The recruitment and study procedures will occur for about 3 years and 3 months. Participants will be asked to participate in the study for a total of six months that may include completing the quitline coaching sessions which can take 1-4 months, Smoke-Free Homes which involves 3 mailings and 1 coaching call over the course of 6 weeks, and follow-up at 3 and 6 months; however, they can withdraw from the study at any time.

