measured by the Heaviness of Smoking Index (cigarettes per day; time elapsed between waking and smoking). These items from the Fagerstrom Test of Nicotine Dependence are reliable over time with good predictive validity. All participants will report use of any pharmacologic cessation aids (i.e., NRT, bupropion, Chantix). Successful quitters (7 days) will report their confidence in staying quit and all others will report readiness to quit. Reactions to the quitline and smoke-free homes interventions and staff will be assessed with measures from our previous studies assessing usefulness (e.g., was it helpful?), satisfaction (would you recommend it to others?) user experience (were they easy to talk to?); coaches (similarity, liking, expertise, sincerity, trustworthiness); and intervention appropriateness (relevant to my life and situation, designed for someone like me). Participants who complete the assessment will be sent a \$25 gift card. Those who didn't quit smoking in the control group will be asked if they would like to try the quitline again. Those who didn't quit who were in the treatment group will be offered whichever program they weren't offered at baseline.

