
**Aim 2.** The primary implementation research question in this Hybrid Type 2 trial is whether demand for and engagement in quitline services – operationalized as acceptance and use – differs by study group. In Aim 2A, the DV is dichotomous (accepts Quitline/does not). Using the same analytical strategies and statistical methods described for Aim 1A, we will examine cumulative probabilities of accepting quitline services during the study period by group, adjusting for baseline covariates. Finding a greater likelihood of accepting quitline services in the combined group (vs. Quitline only) will support our hypothesis. For Aim 2B, the DV is whether participants use 0, 1 or 2+ quitline counseling sessions, and will be treated as an ordinal variable. Counseling sessions include all inbound and outbound phone interactions between a quit coach and participant. Among those who accept quitline services, we will regress number of quitline sessions used by the end of the study on study group and other baseline measures using ordinal logistic regression. The proportional odds assumption will be tested using the score chisquare test. If it is met, adjusted ORs and 95% CIs will be reported from the ordinal logistic regression model. Otherwise, multinomial logistic regression will be used to compare different probabilities (e.g., 0 vs 1 and 0 vs 2+ sessions), adjusting for potential baseline covariates. Finding greater odds of using more sessions in the Quitline and Smoke Free Homes group will support our hypothesis. Aim 2C examines our hypothesis that integrating a Smoke Free Homes intervention into an existing tobacco treatment system will move smokers who are not yet ready to quit incrementally closer to quitting. Readiness to quit, pessimism about quitting and ambivalence about smoking are continuous DVs for this aim. Among participants still smoking at the end of the study, the level of readiness, pessimism and ambivalence at 6-month follow-up will be regressed on study group, states, baseline DV and baseline

characteristics using ordinary least square regression. Finding greater readiness to quit, greater ambivalence about smoking, and less pessimism about quitting in the Quitline and Smoke Free Homes group (vs. Quitline only) would support our hypothesis.

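### Aim 2B compares Quitline session use by arm only among accepters, a group formed after randomisation, and no planned analysis compares use in everyone randomised

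*Combined protocol and SAP*

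**What the plan says.** Section 1.20 (Aim 2) asks whether engagement with the Quitline, "operationalized as acceptance and use", differs by study group, and calls this the primary implementation question.

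- **Acceptance (Aim 2A)** is compared in all participants, cumulatively over the study. The predicted direction is stated: "Finding a greater likelihood of accepting quitline services in the combined group (vs. Quitline only) will support our hypothesis".
- **Use (Aim 2B)** is compared in a subset: "Among those who accept quitline services, we will regress number of quitline sessions used by the end of the study on study group". The model also includes other baseline measures. The result is read as a test of the hypothesis: "Finding greater odds of using more sessions in the Quitline and Smoke Free Homes group will support our hypothesis".
- Section 1.4 poses Aim 2B in the same conditional form: "Among those who accept Quitline services, what proportion use 0, 1, or 2+ sessions of counseling".

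On the order of offers, section 1.7 says: "Participants in Arm 2 will be offered the quitline first and if they decline, they will be offered Smoke-Free Homes". At 3 months, section 1.11 says of Arm 1: "Those who didn't quit smoking in the control group will be asked if they would like to try the quitline again". Of Arm 2 it says: "Those who didn't quit who were in the treatment group will be offered whichever program they weren't offered at baseline". Section 1.21 instead assumes that a second offer of both programs is made at 3 months.

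Intention-to-treat is stated for Aim 1 only. Aim 3 costs the calls but states no comparison of session use by arm. No section compares session use in everyone randomised.

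**The concern.** An accepter is defined by something that happens after assignment and that the intervention is meant to change. If the Aim 2A hypothesis is right, Arm 2's accepters include people whose counterparts in Arm 1 did not accept. Within accepters, arm is then no longer a randomised contrast. Baseline adjustment helps only as far as the covariates explain who accepts.

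The first offer is not the main worry. Arm 2 hears about the Quitline before Smoke-Free Homes, so baseline accepters should be alike, although section 1.20 itself allows, under Aim 1D, that acceptance may differ by group. The later offers are the problem: sessions are counted to the end of the study, and the 3-month offers differ by arm. Read literally, section 1.11 gives Arm 2 decliners no second Quitline offer, since they were already offered both programs at baseline. Section 1.21 assumes they get one. As written, even the direction of the acceptance difference is unclear.

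At stake is the use half of the primary implementation question. Acceptance does not stand in for it, because section 1.21 expects 42% of accepters to take no call.

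**Working it through.** The plan gives no power or expected effect for Aim 2B, so this is an illustration built on its planning figures.

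**Inputs from the protocol.** Section 1.21: 25% accept per offer in both groups; accepters take 0, 1 or 2+ calls in 42%, 31% and 27%, so 58% use at least one; 2% of those who decline quit; 1,980 enrolled (990 per arm if allocation is 1:1); 40% attrition (990 × 0.60 = 594). Section 1.5: 73% reached at 3 months in the ongoing trial.

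**Check on the inputs.** Quit rate among accepters = 0.42×0.12 + 0.31×0.13 + 0.27×0.31 = 0.1744. Quitline-only rate after one offer = 0.25×0.1744 + 0.75×0.02 = 5.86%, matching the stated 5.9%.

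**Assumed, not in the protocol.** The acceptance added by Smoke-Free Homes, and the share *u* of added or later accepters who use at least one session.

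**Arm 1 cumulative acceptance, three versions**
- One offer: 0.25
- Re-offer to decliners still smoking and reached: 0.25 + 0.75×0.98×0.73×0.25 = 0.384
- Re-offer to all decliners: 1 − 0.75² = 0.4375

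**Plan as written in 1.21** (same acceptance and use in both arms): both odds ratios are 1.00. No bias.

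**Case A: Arm 2 decliners are re-offered the Quitline and Smoke-Free Homes adds 10 points of accepters.** Arm 1 use = acceptance × 0.58. Arm 2 use = Arm 1 use + 0.10*u*. Use among Arm 2 accepters = Arm 2 use ÷ (Arm 1 acceptance + 0.10).

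| Arm 1 acceptance | *u* | Any use, all: Arm 1 / Arm 2 | Any use, accepters: Arm 1 / Arm 2 | OR, accepters | OR, all |
|---|---|---|---|---|---|
| 0.25 | 0.58 | 0.145 / 0.203 | 0.580 / 0.580 | 1.00 | 1.50 |
| 0.384 | 0.58 | 0.223 / 0.281 | 0.580 / 0.580 | 1.00 | 1.36 |
| 0.4375 | 0.58 | 0.254 / 0.312 | 0.580 / 0.580 | 1.00 | 1.33 |
| 0.25 | 0.40 | 0.145 / 0.185 | 0.580 / 0.529 | 0.81 | 1.34 |
| 0.384 | 0.40 | 0.223 / 0.263 | 0.580 / 0.543 | 0.86 | 1.24 |
| 0.4375 | 0.40 | 0.254 / 0.294 | 0.580 / 0.547 | 0.87 | 1.22 |

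At *u* = 0.40 and 990 per arm, the accepters-only result is significant in the wrong direction in 18–24% of trials by an unadjusted two-proportion z test. A simulated rank test on 0/1/2+, closer to the planned model, gives 16–21%, and 11–14% with 594 per arm.

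A proportional-odds fit with a different assumed mix agrees. With acceptance of 25% against 35%, and extra accepters at 70/20/10% for 0/1/2+ sessions, any use among Arm 2 accepters is (0.25×0.58 + 0.10×0.30) ÷ 0.35 = 50.0%, against 58.0% in Arm 1. The accepters-only OR is 0.74 and the all-randomised OR is 1.24.

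**Case B: section 1.11 read literally, no added accepters.** Arm 2 acceptance stays at 0.25, so use is 0.25×0.58 = 0.145. Arm 1 gains later accepters L = 0.134 or 0.1875, so its use is 0.145 + L*u*.

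| L | *u* | Any use, all: Arm 1 / Arm 2 | Any use, accepters: Arm 1 / Arm 2 | OR, accepters | OR, all |
|---|---|---|---|---|---|
| 0.134 | 0.58 | 0.223 / 0.145 | 0.580 / 0.580 | 1.00 | 0.59 |
| 0.1875 | 0.58 | 0.254 / 0.145 | 0.580 / 0.580 | 1.00 | 0.50 |
| 0.134 | 0.40 | 0.199 / 0.145 | 0.517 / 0.580 | 1.29 | 0.68 |
| 0.1875 | 0.40 | 0.220 / 0.145 | 0.503 / 0.580 | 1.37 | 0.60 |

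At *u* = 0.40, accepters-only significance in favour of Arm 2 occurs in 34–49% of trials (z test, 990 per arm). The rank test gives 30–44%, and 20–28% with 594. The Aim 2A odds ratio would be 0.53 or 0.43. Arm 1 baseline accepters who try the Quitline again are not modelled.

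**Power in case A** (two-sided 5%, unadjusted z test)

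| Comparison | 990 per arm | 594 per arm |
|---|---|---|
| Aim 2A, +10 points | over 99% | 93–96% |
| Any use, all randomised, *u* = 0.58 | 82–93% | 60–75% |
| Any use, all randomised, *u* = 0.40 | 51–67% | 34–46% |

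With +5 points and 990 per arm, Aim 2A has 61–70% power and any use at *u* = 0.58 has 31–42%.

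**The case against.** The strongest reply is that Aim 2B is declared as a conditional question and answered as one. Acceptance in everyone followed by sessions among accepters is a recognisable two-part analysis, and multiplying the parts gives use across each arm. In case A at 58% use, an odds ratio of 1.00 is the correct answer to that question, and Aim 2A finds the gain with more power than the added model would have. In case B, Aim 2A would point clearly against Arm 2, so someone reading both results would not be misled. The literal reading of section 1.11 may be loose wording, the planned model adjusts for baseline measures, and every departure from 1.00 rests on assumed inputs.

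Much of this stands. The conditional analysis is legitimate and should stay, the plan as a whole would not miss a large gain in acceptance, and the baseline covariates remove some of the selection that the unadjusted figures show. What remains is that section 1.20 asks whether use differs by arm and gives Aim 2B its own rule for supporting the hypothesis, on a comparison that randomisation does not protect. Multiplying the two parts gives an estimate of use by arm, but no test or confidence interval for it is planned.

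**Conclusion.** The concern holds. Use, half of the primary implementation question, has no planned comparison in everyone randomised, and the planned comparison conditions on a post-randomisation event that the plan expects to differ by arm.

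The size of the problem depends on two quantities the protocol does not give: how far acceptance differs by arm, and how much the added or later accepters use the service. If acceptance and mix are equal there is no bias. Over the values tried, Aim 2B ranges from showing no difference when use across the arms differs, to pointing the opposite way. A significant result in the wrong direction is possible but is not the usual outcome in any case examined.

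The change should be made, but the point does not threaten the trial: the primary outcome and sample size are untouched.

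**What to change.** 1. Add the 0/1/2+ ordinal model in all randomised participants, coding non-accepters as 0 sessions, with the planned covariates and the proportional-odds check. Make this the comparison that bears on the use hypothesis.
2. Keep the accepters-only model as the declared conditional question, read descriptively beside Aim 2A.
3. State where session counts come from. If they come from the surveys, say how missing counts are handled.
4. Reconcile sections 1.11 and 1.21 on the 3-month re-offer, because it affects cumulative acceptance by arm.

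The cost is SAP wording and one extra model. The downsides are small. About 75–86% of Arm 1 would have 0 sessions (1 − 0.254 to 1 − 0.145), and the result overlaps with Aim 2A. The gain is smaller if counts exist only for those followed up.

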Aim 1 will use intention-to-treat analyses, providing the most conservative estimate of intervention effects. With randomization and a large sample, we expect baseline characteristics to be similar by group. We will test for this using t-tests for continuous variables and chi-square tests for categorical variables. If significant differences are found, we will include those variables as covariates in all analyses. For Aim 1A (abstinence from smoking) the Cochran-Mantel-Haenszel test will be used to test the conditional association between study group and abstinence at 3- and 6-month follow-up, controlling for states. A Breslow-Day test will be used to examine whether there is a common odds ratio (OR) across states. Finding greater odds of abstinence across states for the group receiving both Quitline and Smoke Free Homes would support the hypothesized intervention effects. If the Breslow-Day test is significant, we will estimate state-specific ORs. To control for other potential covariates, we will regress abstinence at 3- and 6-month follow-up on study group and other covariates using logistic regression. In the regression model, 8 dummy variables for states will be created to account for differences in state Quitlines. Adjusted odds ratios (OR) and 95% confidence intervals (CI) will be reported to quantify the associations. Study group effects for Aim 1B (made a quit attempt or did not) will be examined in a series of analyses similar to those described for Aim 1A. Finding a greater odds of quit attempts in the Quitline and Smoke Free Homes group across states would support hypothesized effects. For Aim 1C, cigarettes smoked per day is a count dependent variable (DV) measured at baseline, 3- and 6-month follow-up and assumed to follow the Poisson distribution. If the assumption of Poisson distribution is met, we will regress the DV on study group, states and other potential covariates and allow the  $\beta$  for study group as a random effect using random-effect Poisson regression. Otherwise, we will fit random effect negative binomial regression to the data. Finding a larger decrease in cigarettes smoked per day in the combined group (vs. Quitline alone) would support the hypothesized effect. Analyses for Aim 1D will replicate those for Aims 1A-C, but be conducted in only the subset of participants from both groups who declined quitline services when offered at baseline. Regression analyses for Aim 1D will also test baseline variables described previously (see "Baseline survey"), because quitline acceptance rates may differ by group. These comparisons provide the best estimate of the added benefit of offering Smoke Free Homes to smokers who are not yet ready to quit.

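### Aim 2B lets a proportional-odds score test, not limited to study group, replace one arm odds ratio with several contrasts, and gives no rule for what then supports the hypothesis

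*Combined protocol and SAP*

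**What the plan says.** Section 1.20 opens Aim 2 with "The primary implementation research question in this Hybrid Type 2 trial is whether demand for and engagement in quitline services", measured by acceptance and use, differs between arms. Aim 2B is the use half. Among participants who accept the quitline, "we will regress number of quitline sessions used by the end of the study on study group and other baseline measures", by ordinal logistic regression with three levels (0, 1, 2+).

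The choice of analysis is then made in two steps. First, "The proportional odds assumption will be tested using the score chisquare test". Then: "If it is met, adjusted ORs and 95% CIs will be reported from the ordinal logistic regression model"; and "Otherwise, multinomial logistic regression will be used to compare different probabilities (e.g., 0 vs 1 and 0 vs 2+ sessions"), with adjustment for baseline covariates.

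The criterion for success is a single sentence: "Finding greater odds of using more sessions in the Quitline and Smoke Free Homes group will support our hypothesis".

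The section does not give a significance level for the score test, say which model terms it covers, or list the baseline measures. The fallback contrasts are offered only as an example. There is no joint test, no multiplicity adjustment, and no rule for contrasts that disagree.

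Two other places bear on this. Section 1.11 allows one to four coaching calls and says details differ between state quitlines. Aim 3 in section 1.20 repeats that the number of calls depends on the state.

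**The concern.** A score test of a model's proportional-odds assumption, with no restriction stated, is most naturally read as covering every term. On that reading, any covariate that acts differently on taking at least one session than on taking two or more can cause rejection. State is an obvious candidate: a quitline offering few calls limits 2+ sessions more than it limits any session. The single arm odds ratio would then be dropped even if the arm effect were exactly proportional.

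After the switch there are at least two arm odds ratios and one success sentence written for a single one. Someone reading the results could count either contrast, require both, or use a joint test. These rules have very different error rates and power, and the choice would be made with the data in view.

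The switch is also not needed to protect the arm test. With no arm effect, the study-group coefficient is zero at both cut-points, so that term satisfies proportional odds whatever the covariates do.

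**Working it through.** **Significance level.** The plan states none, so it was inferred from the Aim 1 sample size in section 1.21 (558 per group, 6% vs 11%, 85% power). With pooled variance under the null and mean proportion 0.085:

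n = [1.96·√(2·0.085·0.915) + 1.036·√(0.06·0.94 + 0.11·0.89)]² / 0.05² = (0.773 + 0.407)² / 0.0025 ≈ 557.1, rounded up to 558.

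The plan's figure is reproduced with two-sided 0.05 and no continuity correction. One-sided gives 446 and continuity-corrected gives 597. Two-sided 0.05 also fits the 95% intervals in "Adjusted odds ratios (OR) and 95% confidence intervals (CI) will be reported to quantify the associations". No power or error rate is stated for Aim 2B.

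**Inputs from section 1.21.** 1,980 enrolled; 25% accept the quitline per offer; 42/31/27% take 0, 1 and 2+ calls.
- Accepters after the first offer: 0.25 × 1,980 = 495.
- Accepters if the same rate applies to a second offer: (0.25 + 0.75 × 0.25) × 1,980 = 0.4375 × 1,980 ≈ 866. This assumes that everyone who declined is reached again, so it is an upper figure.

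**False positives if either contrast counts.** Both contrasts use 0 sessions as reference, so under the null their correlation is

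ρ = (1/p0) / √[(1/p0 + 1/p1)(1/p0 + 1/p2)] = 2.381 / √(5.607 × 6.085) = 2.381 / 5.841 = 0.41.

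P(either significant) = 0.05 + 0.05 − P(both) = 0.10 − 0.0070 = 9.3%. Independent contrasts would give 1 − 0.95² = 9.75%. In the favourable direction only, the rate is 4.6% against 2.5%. Adding 1 vs 2+ as a third contrast gives 12.2%.

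**Simulation.** 2,000 trials per setting, with 9 or 17 model terms. State terms were included in the model; the plan specifies eight state dummies for Aim 1A, and carrying them into Aim 2B is an assumption. The score test covered all terms. The arm effect was always exactly proportional (odds ratio 1.0 or an assumed 1.5). The assumed departures were none, moderate (0.4 on the log-odds of 2+ sessions for states, in one setting with 0.2 for a further covariate) and large (0.8 for states).

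| Result | 495 accepters | 866 accepters |
|---|---|---|
| Switch rate, no departure | 4-6% | 4-5% |
| Switch rate, moderate | 46-53% | 76-84% |
| Switch rate, large | 99% | 100% |
| Ordinal arm test, false positives, all settings | 5.1-5.8% | 4.9-5.7% |
| Two-stage procedure, either contrast counts, no departure | 6.4-6.5% | 5.9-6.1% |
| Two-stage procedure, either contrast counts, departure | 8.8-9.2% | 9.1-9.9% |
| Power at OR 1.5, ordinal arm test | 67-70% | 88-90% |
| Power at OR 1.5, 2-df or Bonferroni | 56-61% | 81-84% |
| Power at OR 1.5, both contrasts required | 21-24% | 41-43% |

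The Monte Carlo standard error of a 5% rate is √(0.05 × 0.95 / 2,000) ≈ 0.5 points.

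The last two power rows apply the fallback to every simulated trial, so they show the cost once a switch happens. Setting by setting, a 2-df or Bonferroni test loses 8-12 points at 495 and 5-7 at 866. Over the whole two-stage procedure with a moderate departure the loss is smaller. For states alone at 495, power is 64-65% against 68%.

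**A second mechanism.** A separate simulation (1,000 data sets per setting, 495 accepters, 16 assumed covariates) gave two covariates an assumed odds ratio of 1.8 on the first step only. The switch rate was 69-72%; with four such covariates it was 97-98%. The either-contrast rate was 8-12% and the ordinal arm test ran at 5-7%.

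**The case against.** Testing proportional odds and naming a multinomial fallback in advance is common practice, and the plan does both. Several further points have force.

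- **Scope of the test.** The plan never says the score test covers all terms; that is inferred from the absence of a restriction. If an arm-only test was meant, covariates would not trigger the switch. The missing rule after the switch would remain.
- **Error rate.** A reader might infer that the plan doubles the false-positive rate. The documents do not support that. It would need a departure large enough to reject, a switch, and a rule that either contrast suffices, and the plan does not state that rule. Even then the figure is 9.3%, because the contrasts are correlated. If both contrasts were required, the error after a switch would be well below 5% (about 1% in the simulations).
- **Assumed sizes.** The departures, the number of covariates and the arm odds ratio of 1.5 are not in the documents. Section 1.21 assumes the same session split in both groups, so it offers no basis for any particular arm effect. With no departure the switch is rare and the overall error is about 6%.
- **Power comparison.** Simulating a proportional arm effect favours a one-parameter ordinal test. A non-proportional arm effect, which is what the fallback is for, was not simulated.
- **Number of accepters.** Sessions are counted to the end of the study, after a second offer, so 495 is the low end and the loss is smaller near 866.

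These points limit the size of the problem. They do not supply the missing decision rule, and they do not show that the switch is needed for a valid arm test. Covariate imbalance between arms among accepters was also checked as a possible threat to the ordinal test; false positives stayed at 4-6.5%.

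**Conclusion.** The point holds as a gap in the decision rule for Aim 2B. An unrestricted score test can replace the single arm odds ratio with contrasts that are not fixed, for reasons unrelated to study arm, and nothing says what then supports the hypothesis. State differences in the number of calls make such a departure plausible, but the documents do not show that it will occur or how large it would be.

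The consequence depends on the rule applied afterwards. Counting either contrast raises the error to about 9%, a joint or Bonferroni test gives up a modest amount of power, and requiring both contrasts costs more than 40 points. The 9.3% follows from the plan's session split and an inferred two-sided 0.05. The switch rates and power losses rest on the assumed departures and the assumed arm odds ratio of 1.5.

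A reader might also infer that this undermines the trial's main result. It does not: the Aim 1 abstinence outcome and its sample size are unaffected. This is a worthwhile, inexpensive improvement to one part of the primary implementation question.

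**What to change.** In section 1.20, Aim 2B:

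1. Make the cumulative-logit odds ratio for study group, with its 95% interval and a stated significance level, the single test of Aim 2B whatever the overall score test shows.
2. List the baseline covariates. Give state unequal slopes in advance (partial proportional odds), and allow unequal slopes for any other covariate that proves non-proportional.
3. Check proportionality for the study-group term only, as an aid to interpretation that does not change the test.
4. Report the multinomial odds ratios (0 vs 1, 0 vs 2+) as descriptive.

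The cost is a few sentences and, with nine states, eight extra state parameters. Freeing other covariates after seeing the data keeps a little data dependence, but the arm test remains one odds ratio. If the arm effect is itself non-proportional, the common odds ratio is an average and must be read beside the descriptive contrasts. A 2-df joint arm test named in advance would also close the gap, at the power cost shown above when the arm effect is proportional.
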